### **3.0 Inclusion/Exclusion Criteria**

Inclusion criteria

- Age  $\geq 18$  years
- Confirmed diagnosis of PD (this will be confirmed by the referring neurologist)
- Hoehn and Yahr stage 1 to 3
- Stable course of disease-modifying therapy over the past 3 months
- MMSE  $\geq 24$
- Neurologist approval for exercise
- Stable deep brain stimulation setting for the past year
- Demonstrate a need for functional rehabilitation

Exclusion criteria

- Severe dyskinesia or severe on-off phenomenon
- Unstable medication regimen
- Any co-morbidity that will interfere with walking
- Conventional physical therapy or G-EO training within the past 6 months
- Height  $<1\text{m}$  or  $>2\text{m}$
- Body weight  $>150\text{ kg}$
- Contraindications to G-EO gait training (e.g., bone instability)

### **4.0 Enrollment/Randomization**

A convenience sample of 30 persons with Parkinson's Disease will be enrolled for this clinical trial. Recruitment will occur through neurologists at the IU Health Neuroscience Center. Each participant will be given time to read the consent form or have it read to them and to ask questions (see Informed Consent Draft). Consent will be obtained before initial assessments and treatment randomization. The consent process will take place at the Indiana Center for Advanced Neurorehabilitation (ICAN) in the Neurorehabilitation and Robotics IU Health Neuroscience Center, [name] [contact].

If found eligible for the study and agree to consent to participate, subjects will be randomized to either conventional physical therapy (CPT) group or CPT with G-EO training using a random numbers generator and concealed allocation.

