### **5.0 Study Procedures**

Screening

Potential subjects will be referred to the study via neurologists at the IU Health Neuroscience Center who specialize in the treatment and management of individuals with Parkinson's disease. A member of the research team will screen the referral by contacting the neurologist and confirming they meet the necessary inclusion and exclusion criteria. Following confirmation of criteria, potential subjects will be contacted by phone to schedule an initial visit for consent and assessment of baseline data.

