
 
• Screening of Inclusion
 
• Informed consent obtained
 
• Random assignment to CPT or GEO
 
	Outcome Measurement 
 
1. Comfortable & Fast Walking Speed/Mechanics 
 
 Trial 1 (14')
 
 Trial 2 (14')
 
 Trial 3 (14')
 
 
 
2. Walking Endurance 
 
 6 MWT
 
 
 
3. Balance 
 
 MiniBESTest
 
 
 
4. LE Strength 
 
 5 times sit to stand test
 
 
 
5. Confidence 
 
 ABC Scale
 
 
 
6. Quality of Life 
 
 PDQ-39
 
 
 
7. Movement agility 
 
o Obstacle Avoidance
 
 
 
8. Performance Assessment 
 
 Accelerometer
 
 
 
	Treatment and control group 2x a week	Outcome Measurement 
 
1. Comfortable & Fast Walking Speed/Mechanics 
 
 Trial 1 (14')
 
 Trial 2 (14')
 
 Trial 3 (14')
 
 
 
2. Walking Endurance 
 
 6 MWT
 
 
 
3. Balance 
 
 MiniBESTest
 
 
 
4. LE Strength 
 
 5 times sit to stand test
 
 
 
5. Confidence 
 
 ABC Scale
 
 
 
6. Quality of Life 
 
 PDQ-39
 
 
 
7. Movement agility 
 
o Obstacle Avoidance
 
 
 
8. Performance Assessment 
 
 Accelerometer
 
 
 
	Outcome Measurement 
 
1. Comfortable & Fast Walking Speed/Mechanics 
 
 Trial 1 (14')
 
 Trial 2 (14')
 
 Trial 3 (14')
 
 
 
2. Walking Endurance 
 
 6 MWT
 
 
 
3. Balance 
 
 MiniBESTest
 
 
 
4. LE Strength 
 
 5 times sit to stand test
 
 
 
5. Confidence 
 
 ABC Scale
 
 
 
6. Quality of Life 
 
 PDQ-39
 
 
 
7. Movement agility 
 
o Obstacle Avoidance
 
 
 
8. Performance Assessment 
 
o Accelerometer
 
 
 

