## **8.0 Statistical Considerations**

Data will be analyzed using IBM SPSS Version 25.0 (IMB Corps., Armonk, NY). Descriptive statistics will characterize the sample on demographic, clinical, safety, and feasibility metrics. We will compare safety and feasibility between groups using chi-square and *t*-tests for independent samples (*Specific Aim 1*). The efficacy of the intervention on study variables (*Specific Aim 2*) will be examined using a 2 (Group) by 2 (Time), mixed factor ANOVA. A completers analysis will be conducted (i.e.,  $\geq 75\%$  of sessions completed). Effect sizes associated with F-statistics will be expressed as eta-squared ( $\eta^2$ ), and effect sizes based on mean differences will be expressed as Cohen's *d*.

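### Section 4.0 states no ratio, block or stratum for 30 participants across three disease stages; followed as written, it leaves an avoidable chance of uneven arms and uneven stage mix

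*Combined protocol and SAP*

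**What the plan says.** The whole description of the method is one sentence in section 4.0 of the combined protocol and SAP: "subjects will be randomized to either conventional physical therapy (CPT) group or CPT with G-EO training", followed by "using a random numbers generator and concealed allocation". The schedule table in section 5.0 adds only "Random assignment to CPT or GEO". No allocation ratio, target per arm, block size, stratification factor or minimisation is stated anywhere. Concealment is stated and is not in question.

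Three other parts of the plan bear on the point:

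- **Size and range.** Section 4.0: "A convenience sample of 30 persons with Parkinson's Disease will be enrolled for this clinical trial". Section 3.0 admits "Hoehn and Yahr stage 1 to 3".
- **When stage is known.** Under Screening in section 5.0, a team member checks eligibility by "contacting the neurologist and confirming they meet the necessary inclusion and exclusion criteria". Stage is one of those criteria, so it is on file before allocation.
- **Analysis.** Section 8.0 says efficacy "will be examined using a 2 (Group) by 2 (Time), mixed factor ANOVA". No severity covariate is named. It also says "A completers analysis will be conducted", restricted to those with at least 75% of sessions.

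**The concern.** With 30 participants, unrestricted allocation often gives visibly unequal arms and can put noticeably more of the advanced patients in one arm. Most outcomes are walking, balance and function measures, and it is plausible that their course over six weeks differs by disease stage. Specific Aim 2 is an efficacy comparison between arms. As written, neither the allocation nor the model controls stage. A chance difference in stage mix could therefore add to, or subtract from, the estimated effect of the G-EO training, and in a sample this small the effect estimate is already imprecise. The completers restriction can unbalance the analysed arms further.

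**Working it through.** The plan gives no derivation for its sample size, so there is no figure of its own to reproduce. The checks take N = 30 from section 4.0 and assume 1:1 allocation.

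**1. Arm sizes under simple randomisation.** P(k : 30−k or worse) = 2 × P(Bin(30, 0.5) ≤ k). Relative efficiency = 4·n1·n2 / 30². Power uses the normal approximation Φ(d / √(1/n1 + 1/n2) − 1.96) with an assumed d = 0.8.

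| Split | Chance of this or worse | Relative efficiency | Power |
|---|---|---|---|
| 15:15 | – | 1.00 | 59.1% |
| 12:18 | 36.2% | 4×12×18/900 = 0.96 | 57.4% |
| 11:19 | 20.0% | 4×11×19/900 = 0.93 | 56.0% |
| 10:20 | 9.9% | 4×10×20/900 = 0.89 | 54.2% |

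Uneven arms are likely, but they cost only about 2 points of power at 12:18 and 5 points at 10:20.

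**2. Stage mix under simple randomisation.** The documents give no stage distribution, so let S be the number at stage 3 and vary it. The stage-3 count in one arm is a ~ Bin(S, 0.5), and the count of others in that arm is b ~ Bin(30−S, 0.5), independently. The gap in stage-3 share is |a/(a+b) − (S−a)/(30−a−b)|. Exact enumeration gives:

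| S | 8 | 9 | 10 | 11 | 12 | 13 | 14 | 15 |
|---|---|---|---|---|---|---|---|---|
| P(gap ≥ 20 points) | 24% | 27% | 26% | 30% | 29% | 31% | 29% | 36% |

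**3. What reaches the planned test.** With two time points, the Group by Time test is equivalent to a t-test on change scores. Let stage 3 differ from stages 1-2 by λ in level at both times and by δ in mean change, and let p1 and p2 be the stage-3 shares of the two arms. Then the expected difference in mean change, given the shares, is the treatment effect + δ·(p1 − p2). The λ term cancels. For a 20-point gap the shift is 0.20·δ. If δ is 0.5 to 1.0 SD of change (an assumption), the shift is 0.10 to 0.20 SD, against a standard error of √(2/15) = 0.365 SD in arms of 15.

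**4. What restriction achieves.** Forcing 15:15 without strata removes the size imbalance, but for S = 8 to 15 it still leaves a 21% to 47% chance of a 20-point stage gap (hypergeometric). With two strata (stages 1-2 and stage 3) and blocks of 2 and 4, each stratum can be off by at most 2. The total difference is then at most 4, or 13:17. Simulation over S = 8 to 15 agreed, with a largest stage-3 share gap of about 13 points (2/15). With blocks of 4 and 6, each stratum can be off by 3, so the bound is a difference of 6, or 12:18. In 10,000 simulated runs for each S, that split appeared in at most 4 runs.

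**The case against.** The strongest reply has four parts.

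**The text is silent; it does not prohibit restriction.** A permuted-block list is also produced from random numbers. A reader might infer that the sponsor chose unrestricted allocation, but the documents do not establish that. What stands is that someone following the text has no ratio, block or stratum to apply.

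**Stage differences in level do not matter here.** A reader might reason that if stage 3 patients walk 1 SD worse, a 7:3 split in arms of 15 shifts the result by (7−3)/15 = 0.27 SD. That holds for a comparison of post-treatment levels. In the planned Group by Time test a constant level difference cancels. This objection stands in full, and only differential change remains.

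**Counting stage-3 patients exaggerates the risk.** With 10 at stage 3, a split of 7:3 or worse has probability 34%, but that ignores arm size: 7 of 20 against 3 of 10 is 35% against 30%, nearly balanced. The chance of a share gap of 4/15 or more is 15.8%. This also stands, which is why the working uses shares.

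**Chance imbalance is not bias.** Randomisation keeps the test valid, and the standard error already reflects chance imbalance. Baseline values will be measured and the sample described, so a reader could see an imbalance. All true. It does not answer why an avoidable source of variation should be left in when the stratifier is already to hand.

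**Conclusion.** The point holds as an inexpensive improvement to design and analysis, not as a flaw that invalidates the trial. Read as written, section 4.0 gives a 36% chance of arms of 12:18 or worse and, for 8 to 15 stage-3 participants, roughly a 24% to 36% chance of a stage-3 share gap of 20 points or more. The harm is a modest loss of precision and possible chance confounding if change over time differs by stage. The documents do not support calling this systematic bias, or a serious loss of power.

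The size rests on three assumptions: 1:1 allocation, no undisclosed restriction, and a stage mix the documents do not give. Whether change differs by stage is also not documented.

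**What to change.** - **Allocation.** State in section 4.0 a computer-generated 1:1 list in permuted blocks of varying size, stratified by Hoehn and Yahr 1-2 versus 3. Keep the list concealed and the block sizes undisclosed, and have it held by someone outside referral, treatment and assessment. Use one factor with two levels only; three separate stage strata with blocks of 4 could still end at 12:18.
- **Analysis.** Include the stage stratum and its interaction with time in the efficacy model of section 8.0. This is the same as adjusting the change-score comparison for stage, and takes one degree of freedom (28 to 27 with all 30 analysed). It also gives some protection in the completers set, where balance by design may be lost.
- **Cost.** A different list and one line of analysis text. The real downside is predictability near block ends, because treating therapists at the single centre know the allocation; in a block of 2 the second assignment follows from the first. Avoiding blocks of 2, for example by using 4 and 6, reduces this at the price of slightly looser balance (up to 12:18, rarely).
- **If enrolment has begun.** Document the method actually used, including any restriction, and prespecify stage in the model before outcome data are examined.

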### **5.0 Study Procedures**

Screening

Potential subjects will be referred to the study via neurologists at the IU Health Neuroscience Center who specialize in the treatment and management of individuals with Parkinson's disease. A member of the research team will screen the referral by contacting the neurologist and confirming they meet the necessary inclusion and exclusion criteria. Following confirmation of criteria, potential subjects will be contacted by phone to schedule an initial visit for consent and assessment of baseline data.

### **Assessments**

The study outcomes will be collected by treatment-blinded researchers. All participants on Day 1 who consent to be in the study will complete the following mobility outcomes:

1. Spatial and temporal gait kinematics will be assessed using a PKMAS Zeno Walkway (Protokinetics). Participants will be asked to walk over a 14-foot pressure mat that will capture their gait kinematics and speed. Comfortable and fast walking speed will be assessed. (10 minutes)
2. A 6-minute walk (6MWT) tests to determine walking endurance. Subjects will be asked to walk for 6 minutes along a 30m track. Subjects may stop and rest as often as needed. Subject walking speed will be collected during the test to evaluate rate of functional fatigue. (10 minutes)
3. Balance assessment using the Mini BESTest. Subjects will be asked to complete 14 different tasks ranging from static standing to dynamic walking. All subjects will be guarded closely for safety to prevent falling. (15 minutes)
4. The level of lower extremity functional strength combined with balance will be assessed by the five times sit to stand test. (5 minutes)
5. Performance translation of balance improvement will be measured using the self-report Activities Balance Confidence Scale. (10 minutes)
6. Their level of health-related quality of life assessed by the Parkinson's disease Questionnaire-39. (15 minutes)
7. Obstacle management while walking. Patients will be asked to walk over a flat firm surface for 14 meters. The pathway will include a box that is one foot by one foot that each person. (6 passes; 10 minute break; 6 passes; 10 minute break; 6 passes; 10 minute break) total of 40 minutes
8. Performance translation to real life activities will be measured by accelerometers. Each participant will wear an accelerometer at home to measure activity levels. (completed at home)
- After completing all of therapy, the research team will complete a short interview with the participant. The interview will focus on their experiences during therapy regardless of which group they participated in. We will also ask them to consider how valuable they think the experience was for their health. This interview will take about 15 minutes.

Participants will complete outcome assessments prior to the start of the study, at the end, and one month following completion.

### **Schedule**

Following completion of day 1 assessments, all subjects will be scheduled for the intervention phase of the study. Regardless of group allocation, each participant will receive 12 total visits scheduled ideally two times a week for 6 weeks. Following completion of the 12 visits each subject will complete all outcome assessments. (See Table 1) If a subject cancels a treatment session, it will be rescheduled to ensure that all subjects complete the total of 12 treatment sessions prior to final testing. If a subject misses three consecutive treatment sessions, they will be dropped from the study due to inconsistency in treatment carryover. Cancellations and changes

in patient scheduling is a part of true clinical experience and represents normal clinical patient management. Therefore, the emphasis is on total number of treatments (12) and not on total number of weeks.

Pre-Intervention Phase		Intervention Phase	Post Intervention	Follow Up
Day 1	Day 2 Measurement	6 weeks intervention period	Post Assessment	 Month Follow Up

 
• Screening of Inclusion
 
• Informed consent obtained
 
• Random assignment to CPT or GEO
 
	Outcome Measurement 
 
1. Comfortable & Fast Walking Speed/Mechanics 
 
 Trial 1 (14')
 
 Trial 2 (14')
 
 Trial 3 (14')
 
 
 
2. Walking Endurance 
 
 6 MWT
 
 
 
3. Balance 
 
 MiniBESTest
 
 
 
4. LE Strength 
 
 5 times sit to stand test
 
 
 
5. Confidence 
 
 ABC Scale
 
 
 
6. Quality of Life 
 
 PDQ-39
 
 
 
7. Movement agility 
 
o Obstacle Avoidance
 
 
 
8. Performance Assessment 
 
 Accelerometer
 
 
 
	Treatment and control group 2x a week	Outcome Measurement 
 
1. Comfortable & Fast Walking Speed/Mechanics 
 
 Trial 1 (14')
 
 Trial 2 (14')
 
 Trial 3 (14')
 
 
 
2. Walking Endurance 
 
 6 MWT
 
 
 
3. Balance 
 
 MiniBESTest
 
 
 
4. LE Strength 
 
 5 times sit to stand test
 
 
 
5. Confidence 
 
 ABC Scale
 
 
 
6. Quality of Life 
 
 PDQ-39
 
 
 
7. Movement agility 
 
o Obstacle Avoidance
 
 
 
8. Performance Assessment 
 
 Accelerometer
 
 
 
	Outcome Measurement 
 
1. Comfortable & Fast Walking Speed/Mechanics 
 
 Trial 1 (14')
 
 Trial 2 (14')
 
 Trial 3 (14')
 
 
 
2. Walking Endurance 
 
 6 MWT
 
 
 
3. Balance 
 
 MiniBESTest
 
 
 
4. LE Strength 
 
 5 times sit to stand test
 
 
 
5. Confidence 
 
 ABC Scale
 
 
 
6. Quality of Life 
 
 PDQ-39
 
 
 
7. Movement agility 
 
o Obstacle Avoidance
 
 
 
8. Performance Assessment 
 
o Accelerometer
 
 
 

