## **7.0 Study Withdrawal/Discontinuation**

Participants may withdraw from the study at any time by contacting the program manager ([name]) of Neurorehabilitation and Robotics at [contact]. Additionally, participants may communicate their desire to withdraw from the study to any of the study's investigator: [name] [contact]).

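### Participants who miss three sessions in a row leave the study with no planned outcome assessment, so the Aim 2 comparison would exclude randomised people according to attendance

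*Combined protocol and SAP*

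**What the plan says.** Section 5.0 (Schedule) sets the removal rule: "If a subject misses three consecutive treatment sessions, they will be dropped from the study due to inconsistency in treatment carryover". The same section ties post-testing to finishing treatment: "Following completion of the 12 visits each subject will complete all outcome assessments". It treats cancellations separately: "If a subject cancels a treatment session, it will be rescheduled to ensure that all subjects complete the total of 12 treatment sessions". It adds that "the emphasis is on total number of treatments (12) and not on total number of weeks".

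Section 5.0 (Assessments) gives three time points: "Participants will complete outcome assessments prior to the start of the study, at the end, and one month following completion". Neither that section nor the schedule table has a visit for people who stop early. Section 7.0 explains how a person may leave ("Participants may withdraw from the study at any time by contacting the program manager") and says nothing about later assessment.

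Section 8.0 says that efficacy "will be examined using a 2 (Group) by 2 (Time), mixed factor ANOVA". It continues: "A completers analysis will be conducted", with a threshold of at least 75% of sessions. It names no as-randomised analysis set and no method for missing outcomes.

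Section 5.0 (Feasibility and Safety) makes retention and adherence feasibility outcomes, and Section 8.0 compares feasibility between the groups.

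**The concern.** The stated reason for the rule concerns treatment exposure. That can justify stopping training, or a secondary analysis of people who were adequately treated. It does not justify ending outcome collection, which is what removal from the study does.

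Attendance is observed after randomisation. Therapists and participants know which training is given; only the outcome assessors are described as blinded. Section 6.0 monitors for soreness, fatigue and falls, which are plausible reasons for absence and may be related to outcome. If people lost from the two arms differ in number or kind, the groups compared under Aim 2 are no longer the groups that were randomised. The documents do not show that this will happen, but they leave it open. An outcome that was never collected cannot be recovered at the analysis stage.

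**Working it through.** **No planned figure to reproduce.** The documents give no miss rate, dropout rate, standard deviation (SD) or power calculation. The 30 is described as a convenience sample. Everything numerical below is illustrative.

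**Step 1: does a removed person have a post value?** The Schedule text removes the person and triggers post-testing by the twelfth visit. The Assessments text and the schedule table add no early visit, and Section 7.0 adds none. So no post value is planned. A standard mixed-factor ANOVA on two times needs both values from each person, so without a missing-data method the person is left out.

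**Step 2: how many people?** Inputs: 12 sessions and 30 people (from the documents); per-session miss probability p, independent between sessions (assumed). If missed sessions are made up until 12 are attended, each attended session must be reached before a run of three misses, which occurs with probability p³. Hence

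P(removed) = 1 − (1 − p³)^12.

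For p = 0.10, this is 1 − 0.999^12 = 0.0119, and 0.0119 × 30 = 0.36 people. The alternative of 12 fixed slots with no make-up sessions is the probability of a run of three misses in 12 trials.

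| Assumed p | Removed, sessions made up | Of 30 | Removed, 12 fixed slots | Of 30 |
|---|---|---|---|---|
| 5% | 0.15% | 0.04 | 0.12% | 0.04 |
| 10% | 1.2% | 0.36 | 0.9% | 0.27 |
| 20% | 9.2% | 2.8 | 6.5% | 1.9 |
| 30% | 28.0% | 8.4 | 18.9% | 5.7 |

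The 30% row is reached only if cancellations that are rescheduled also count as misses. The Schedule text treats the two separately, though it does not define a miss.

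**Step 3: precision, if loss is equal in both arms and unrelated to outcome.** With 15 per arm (1:1 assumed; the ratio is not stated) and loss fraction d, the standard error of the group difference in SD units is √(2 / [15(1 − d)]). With d = 0 it is 0.365. At p = 5%, 10% and 20% it rises by 0.1%, 0.6% and 4.9%; the last gives 0.383.

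**Step 4: bias.** Let q be the share removed in an arm and g the mean change of those retained minus that of those removed, in SD. The retained mean exceeds the arm's full mean by q × g, so the group difference shifts by q₁g₁ − q₂g₂. With equal q and equal g this is zero. If only one arm loses people and g is between 0.5 and 1.0 SD (assumed):

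- 2 of 15 removed: (2/15) × 0.5 to (2/15) × 1.0 = 0.07 to 0.13 SD.
- 3 of 15 removed: 0.20 × 0.5 to 0.20 × 1.0 = 0.10 to 0.20 SD.

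**Step 5: fit with the completers threshold.** 75% of 12 is 9 sessions. A person who attends nine to eleven sessions and then misses three in a row meets the threshold but is removed without post data. The chance is (1 − p³)^9 × [1 − (1 − p³)^3]: 0.04%, 0.3% and 2.2% at p = 5%, 10% and 20%, at most 0.66 people of 30. Conversely, if everyone tested has completed 12 visits, the threshold excludes nobody. The rules in Sections 5.0 and 8.0 therefore need to be reconciled.

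**The case against.** **The ANOVA may be meant to include everyone.** Section 8.0 does not say whom the ANOVA covers, and the completers analysis can be read as an addition to an analysis of all available people. The 75% threshold has a purpose only if some people with fewer than 12 sessions are tested, and the Assessments text is not limited to completers. This stands in part: omission from the ANOVA is an inference, not stated text. It does not remove the point, because even an all-randomised analysis would have no planned post value for a removed person.

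**Rescheduling protects participants.** It protects those who cancel and then attend. It does not protect those who miss three in a row.

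**Differential loss is already monitored.** This is correct, and it matters. Retention and adherence are feasibility outcomes compared by group, so unequal retention would be seen. Seeing it does not correct the efficacy comparison. Equal rates with different reasons for loss would not show up in a comparison of rates.

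**This is a small study centred on feasibility.** That is fair as to weight. Aim 2 nevertheless sets out to determine efficacy from a randomised comparison.

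**A stronger reading a reader might draw** is that the plan will lose a quarter or more of its participants, or that the error rate is badly inflated. The 28% figure requires counting rescheduled cancellations as misses, against the way the Schedule separates them. If exactly the worst 2, 3 or 5 of 15 in one arm only were lost, with no true effect, simulated type I error would be about 10%, 16% or 28%. That is a deliberately extreme case, not an estimate, and nothing in the documents suggests it.

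**Conclusion.** The concern holds in conditional form. Followed as written, the plan removes randomised people from the study for poor attendance and arranges no outcome assessment for them. Unless they are assessed anyway, the Aim 2 comparison excludes them.

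The size cannot be fixed from the documents. Under independent misses at 5% to 10% per session the effect is negligible: fewer than one person of 30. At 20% it is about three people, with a 4.9% larger standard error if loss is balanced. Absences caused by illness tend to cluster, so the independence model may misstate the risk. Neither the direction nor the size of any bias can be determined. It would be zero with equal loss and equal outcome gaps in the two arms.

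The documents do not support saying that the ANOVA certainly omits these people, that the comparison is biased, or that all the missing data could be avoided. This is a cheap improvement worth making before enrolment, not a flaw that invalidates the trial.

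**What to change.** **Section 5.0 (Schedule).** Replace removal from the study with: training stops; the participant stays in the study and is invited to the post assessment (6 weeks after the first session, or within 1 week of stopping if that is later) and to the 1-month assessment. People who finish all 12 visits keep the present timing. State that a rescheduled cancellation is not a miss.

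**Section 8.0.** Make the main Aim 2 analysis all randomised participants with outcome data, by assigned group. Label the completers analysis (at least 75% of sessions) supplementary. Report reasons for missing outcomes by arm, alongside the retention comparison already planned. A mixed model is optional: someone with only a baseline value adds little to the change contrast, so collecting the assessments is the main remedy.

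**Cost.** The change is to wording, plus follow-up of the few who stop training. Each would be asked for up to two further batteries of about 105 minutes (10 + 10 + 15 + 5 + 10 + 15 + 40, from the Assessments list), plus the accelerometer at home. Some will decline, so missing data will fall but not disappear. Post-assessment timing will vary somewhat between those who stop and those whose 12 visits take longer than 6 weeks.

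### Table 1 randomises on Day 1 and measures baseline on Day 2, the text puts baseline on Day 1, and nothing requires baseline to be complete before participants learn their arm

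*Combined protocol and SAP*

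**What the plan says.** The protocol gives two accounts of the days before treatment.

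- **Table 1 (Section 5.0, Schedule).** The Day 1 cell holds screening, consent and "Random assignment to CPT or GEO". The full outcome battery sits in the next column, headed "Day 2 Measurement".
- **Section 5.0, Screening.** Candidates are phoned to "schedule an initial visit for consent and assessment of baseline data", which is one visit for both.
- **Section 5.0, Assessments.** "All participants on Day 1 who consent to be in the study will complete the following mobility outcomes".
- **Section 5.0, Schedule, text.** "Following completion of day 1 assessments, all subjects will be scheduled for the intervention phase of the study".
- **Section 4.0.** "Consent will be obtained before initial assessments and treatment randomization". Allocation is made "using a random numbers generator and concealed allocation".
- **Section 5.0, Assessments, closing line.** "Participants will complete outcome assessments prior to the start of the study, at the end, and one month following completion". This ties baseline to the start of the study, not to randomisation.

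Section 2.0 calls the trial single-blinded, and the Assessments text names the outcome researchers as the blinded party. The battery includes the ABC Scale and PDQ-39, walking tests including the 6-minute walk, and an accelerometer worn at home. Section 8.0 tests efficacy with a Group (2) by Time (2) mixed ANOVA and does not name the two Time levels.

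**The concern.** Table 1 is the only place that puts randomisation and baseline measurement in sequence, and it puts randomisation first. The two arms look plainly different to the person being treated: a harness and driven footplates in one, overground walking in the other. The protocol does not describe participants as blinded, and it does not say that the assignment is withheld from them until baseline is complete.

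A participant who already knows the arm may rate balance confidence or quality of life differently, try more or less hard in a walking test, or be more or less active at home. Blinded assessors guard against observer bias but not against this. Concealed allocation guards the decision to enrol, not measurements taken after assignment.

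Two things are at stake. The baseline could differ between arms for a reason other than chance, and a Group by Time test would carry that difference into the treatment effect. Also, a person randomised on Day 1 who leaves before Day 2 has no baseline and cannot contribute to that test.

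**Working it through.** **1. Order of events, by source**

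| Source | Consent | Randomisation | Baseline battery |
|---|---|---|---|
| Table 1 | Day 1 | Day 1 | Day 2 |
| Screening text | initial visit | not placed | initial visit |
| Assessments text | Day 1 | not placed | Day 1 |
| Schedule text | – | not placed | Day 1, before treatment is scheduled |
| Section 4.0 | first | after consent | after consent |

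The day of baseline is contradictory. The order of randomisation and baseline is explicit only in Table 1. Section 4.0 names assessments before randomisation but states only that consent precedes both.

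The accelerometer is a special case. Its baseline is collected at home, so a Day 1 assignment would come before that measure is complete even if the rest of the battery is done on Day 1.

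**2. Effect on the estimate**

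Take the two Time levels to be baseline and post-treatment (inferred). The Group by Time contrast is

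(post_GEO − pre_GEO) − (post_CPT − pre_CPT).

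Suppose knowing the arm shifts one arm's baseline by b, and a fraction p of that shift is still present at post-test. The contrast then moves by b(1 − p) in size.

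- p = 0: it moves by the full b.
- p = 1: the shift cancels.
- In between: part of it enters.

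The sign depends on the arm and the direction. If CPT participants are disappointed and look worse at baseline, their change looks larger and the estimate moves against G-EO. If G-EO participants look worse at baseline, it moves in favour of G-EO.

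**3. Illustration of size**

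The protocol gives no b, no pre-post correlation r and no power calculation. It gives a sample of 30. Assumptions: 15 per arm, equal SD at both times, b = 0.2 SD, p = 0, and r from 0.5 to 0.9.

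- SE of the difference in change, in SD units: √[2(1 − r) × 2/15]
- Two-sided rejection rate with no true effect: P(|Z + b/SE| > 1.96)

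| r | SE | b/SE | Rejection rate (normal) | Rejection rate (t, 28 df) |
|---|---|---|---|---|
| 0.5 | 0.365 | 0.55 | 8.5% | 8.3% |
| 0.7 | 0.283 | 0.71 | 10.9% | 10.5% |
| 0.9 | 0.163 | 1.22 | 23.2% | 21.9% |

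At r = 0.7, other assumed shifts give 6.4% (0.1 SD) and 18.5% (0.3 SD) by the normal formula. A 0.2 SD shift of which half persists acts as 0.2 × (1 − 0.5) = 0.1 SD, which gives 6.4%.

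**4. Which tail**

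At r = 0.7 and b = 0.2 SD, the 10.9% splits into 10.5% in the direction of the shift and 0.4% in the other. With no shift, each tail holds 2.5%. Under the disappointed-control mechanism the larger tail is a false finding for CPT, and the chance of falsely favouring G-EO falls from 2.5% to 0.4%.

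**The case against.** The strongest reply is that this is an inconsistency in a table, not a demonstrated bias. Harm needs three things together: the site follows Table 1 over the text, the assignment is disclosed and not merely generated on Day 1, and knowing the arm changes the baseline. The text leans the other way, with one visit for consent and baseline, and Section 4.0 naming assessments before randomisation. Assessors are blinded, and both arms get 12 sessions of matched time, so selective withdrawal between Day 1 and Day 2 is conjecture. The trial is a 30-person convenience sample whose first aim is safety and feasibility.

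Most of this stands. It limits how strongly the consequence can be stated. It does not remove the contradiction, and a lean in the wording is not a requirement that baseline be complete first.

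Three stronger readings are tempting, and the documents do not support them:

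- **That baselines will be taken after participants know their arm.** No section says when they are told.
- **That any baseline shift enters the effect in full.** This holds only if the shift has gone by post-test. Knowledge of the arm lasts through the trial, so some of the shift may persist and cancel.
- **That the error would flatter G-EO.** The most natural mechanism, disappointment in the control arm, works against it.

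**Conclusion.** The concern holds as a conflict in the stated sequence that leaves an avoidable route to bias open. Table 1 and the text of Section 5.0 disagree on the day of baseline, and neither Section 4.0 nor Section 5.0 requires baseline to be complete before assignment. A site that follows Table 1 and discloses on Day 1 would take self-reported, effort-dependent and home-activity baselines from people who know their arm, and could have randomised participants with no baseline.

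The size cannot be had from the documents. The 8% to 23% range illustrates one assumed case (0.2 SD, none of it persisting, 15 per arm, correlation 0.5 to 0.9); it is not an estimate for this trial. That participants are unblinded is itself inferred, from the single-blind design, the naming of assessors as the blinded role and the visible difference between treatments.

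This should be fixed, because a baseline taken after disclosure cannot be recovered in the analysis. It does not make the planned comparison invalid as it stands.

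**What to change.** Reconcile Table 1 with Sections 4.0 and 5.0 so that all give the same day for baseline and the same order of events. Add one sentence to Section 4.0 and mirror it in Table 1, for example: Random assignment is generated or disclosed only after all baseline outcome measures are complete, including the home accelerometer wear period. In Table 1, move the random-assignment line to after the baseline battery.

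If enrolment has begun, record for each participant the dates of baseline, assignment and disclosure, and report the sequence actually used.

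The cost is mostly wording and the moving of one step. It may not be free: because the accelerometer is worn at home, waiting for its data could mean a short delay or a device-return step before allocation. The change protects the baseline only. Participants will still know their arm at post-test and follow-up.
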